5.2.2.2. Geometric Means

The geometric means will be calculated as the mean of the assay results after making the logarithm transformation and then exponentiating the mean to express results on the original scale. Two-sided 95% CIs will be obtained by taking log transforms of assay results, calculating the 95% CI with reference to Student's t distribution, and then exponentiating the confidence limits.

5.2.2.3. Geometric Mean Fold Rises

GMFRs are defined as ratios of the results after vaccination to the results before vaccination. GMFRs are limited to participants with nonmissing values at both time points.

GMFRs will be calculated as the mean of the difference of logarithmically transformed assay results (later time point minus earlier time point) and exponentiating the mean. The associated 2-sided 95% CIs will be obtained by constructing CIs using Student's t distribution for the mean difference on the logarithm scale and exponentiating the confidence limits.

5.2.2.4. Reverse Cumulative Distribution Curves

Empirical RCDCs will plot proportions of participants with values equal to or exceeding a specified assay value versus the indicated assay value, for all observed assay values. Data points will be joined by a step function with data points on the left side of the step.

5.3. Methods to Manage Missing Data

A partial AE start date (missing day or missing both month and day) will be imputed by assigning the earliest possible start date using all available information, such as the stop date of the AE and the vaccination date(s) from the same participant, following the Pfizer standard for handling incomplete AE start date. A complete missing start date for an AE is not allowed in the data collection.

Missing serology results will not be imputed. Immunogenicity results that are below the LLOQ will be set to $0.5 \times \text{LLOQ}$ in the analysis; this may be adjusted once additional data on the assay characteristics become available.

No additional imputation will be applied to other missing data.

6. ANALYSES AND SUMMARIES

6.1. Primary Endpoints

6.1.1. Primary Safety Endpoints

6.1.1.1. Local Reactions

6.1.1.1.1. Main Analysis

- Estimands: The percentage of participants reporting local reactions (redness, swelling, and pain at the injection site) within 7 days after each vaccination ([Section 2.1](#)).
- Analysis set: Safety population ([Section 4](#)).
- Analysis time point: Within 7 days after each vaccination.
- Analysis methodology: Descriptive statistics ([Section 5.2.1](#)).
- Intercurrent events and missing data: The participants without any e-diary data throughout the 7 days after vaccination will be excluded from the analysis at that particular vaccination; missing values will not be imputed.
- Reporting results: Descriptive statistics for each and any local reaction after each vaccination in each vaccine group will be presented by maximum severity and cumulatively across severity levels. Confirmed e-diary errors will be excluded from the analysis. Descriptive summary statistics will include counts and percentages of participants with the indicated endpoint and the associated 2-sided Clopper-Pearson 95% CIs.

6.1.1.1.2. Supplemental Analyses

To support the assessment of local reactions, the following endpoints (as defined in [Section 3.1.1.1](#)) will be summarized with the same analysis time point and analysis population as above, and appropriate analysis methodology and reporting results. Confirmed e-diary errors will be excluded from these analyses.

- Duration (days) of each local reaction after each vaccination.
- Onset day of each local reaction after each vaccination.

These continuous endpoints will be summarized by displaying n, mean, median, standard deviation, minimum, and maximum for each vaccination, by vaccine group.

Figures:

Bar charts with the proportions of participants for each local reaction throughout 7 days after each vaccination will be plotted for each vaccination, by vaccine group. The bars will be divided into severity categories to highlight the proportions of participants by maximum severity.

6.1.1.2. Systemic Events

6.1.1.2.1. Main Analysis

- Estimands: The percentage of participants reporting systemic events (fever, fatigue/tiredness, headache, chills, vomiting, diarrhea, new or worsened muscle pain, and new or worsened joint pain) within 7 days after each vaccination ([Section 2.1](#)).
- Analysis set: Safety population ([Section 4](#)).
- Analysis time point: Within 7 days after each vaccination.
- Analysis methodology: Descriptive statistics ([Section 5.2.1](#)).
- Intercurrent events and missing data: The participants without any e-diary data throughout the 7 days after vaccination will be excluded from the analysis at that particular vaccination; missing values will not be imputed.
- Reporting results: Descriptive statistics for each systemic event after each vaccination in each vaccine group will be presented by maximum severity and cumulatively across severity levels. Descriptive summary statistics will include counts and percentages of participants with the indicated endpoint and the associated 2-sided Clopper-Pearson 95% CIs.

6.1.1.2.2. Supplemental Analyses

The following endpoints for assessment of systemic events will be summarized similarly to the assessment of local reactions:

- Duration of each systemic event after each vaccination.
- Onset day of each systemic event after each vaccination.

These continuous endpoints will be summarized by displaying n, mean, median, standard deviation, minimum, and maximum for each vaccination, by vaccine group.

The use of antipyretic medication (see [Section 3.1.1.3](#)) will be summarized similarly to systemic events, except that there is no severity level associated with the use of antipyretic medication.

In addition, the proportions of participants reporting each prompted systemic event after any vaccination will be summarized by maximum severity level.

Figures:

Bar charts with the proportions of participants reporting each systemic event throughout 7 days will be plotted for each vaccine group. The bars will be divided into severity categories to highlight the proportions of participants by maximum severity.

6.1.1.3. Adverse Events

6.1.1.3.1. Main Analysis

- Estimand: The percentage of participants reporting AEs within 1 month after each vaccination ([Section 2.1](#)).
- Analysis set: Safety population ([Section 4](#)).
- Analysis time point: Within 1 month after each vaccination.
- Analysis methodology: Descriptive statistics on a 3-tier approach ([Section 5.2.1](#) and [Section 3.1.1.4](#)).
- Intercurrent events and missing data: Missing data will not be imputed except for partial AE start dates ([Section 5.3](#)).

- Reporting results: Counts, percentages, and the associated 2-sided Clopper-Pearson 95% CIs of AEs within 1 month after each vaccination will be provided for each vaccine group. For both Tier 1 (if any) and Tier 2 events, the between-group difference in proportions and the associated 2-sided 95% CI based on the Miettinen and Nurminen² method will be provided for 1 month after vaccination with SIV and BNT162b2 at Visit 1 for the coadministration group vs 1 month after vaccination with SIV and saline at Visit 1 for the separate-administration group, and for 1 month after vaccination with SIV and BNT162b2 at Visit 1 for the coadministration group vs 1 month after vaccination with BNT162b2 at Visit 2 for the separate-administration group. For Tier 1 events (if any), the asymptotic p-values for the difference in proportions will be provided, based on the same test statistic and under the assumption that the test statistic is asymptotically normally distributed. For Tier 3 events, counts and percentages will be provided for each vaccination in each vaccine group.

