1.3. Schedule of Activities

The SoA table provides an overview of the protocol visits and procedures. Refer to the [STUDY ASSESSMENTS AND PROCEDURES](#) section of the protocol for detailed information on each procedure and assessment required for compliance with the protocol.

The investigator may schedule visits (unplanned visits) in addition to those listed in the SoA table, in order to conduct evaluations or assessments required to protect the well-being of the participant.

Visit Number	1	2	3
Visit Description	Vaccination 1	Vaccination 2	Follow-Up After Vaccination 2
Visit Window	Day 1	28 to 42 Days After Vaccination 1	28 to 42 Days After Vaccination 2
Obtain informed consent	X		
Assign participant number	X		
Obtain demography and medical history data	X		
Perform clinical assessment ^a	X		
Record BNT162b2 vaccine history	X		
Collect and record nonstudy vaccinations	X	X	X
Measure temperature (oral)	X	X	
Perform urine pregnancy test (if appropriate)	X	X	
Confirm use of contraceptives (if appropriate)	X	X	X
Collect prohibited medication use	X	X	X
Confirm eligibility	X	X	
Review temporary delay criteria	X	X	
Obtain randomization number	X		
Obtain study intervention container allocation using the IRT system	X	X	

Visit Number	1	2	3
Visit Description	Vaccination 1	Vaccination 2	Follow-Up After Vaccination 2
Visit Window	Day 1	28 to 42 Days After Vaccination 1	28 to 42 Days After Vaccination 2
For participants who are HIV-positive, record latest HIV viral load and CD4 count	X		X
Collect blood sample for immunogenicity assessment	30 mL	30 mL	30 mL
Administer study intervention	X	X	
Assess acute reactions for at least 30 minutes after study intervention administration	X	X	
Explain/review participant communication methods (including for reactogenicity e-diary completion), assist the participant with downloading the app, or issue provisioned device, if required	X	X	
Provide/ensure participant has a thermometer and measuring device	X	X	
Review reactogenicity e-diary data (daily review is optimal during the active diary period)	X	X	
Review ongoing reactogenicity e-diary symptoms with participant and obtain stop dates		X	X
Ask the participant to contact the site staff or investigator if the participant experiences acute chest pain, shortness of breath, or palpitations.	X	X	
Collect AEs and SAEs	X	X	X
Request the participant return the e-diary or assist the participant to delete the application			X

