
Participants will be required to attend healthcare facilities during the global SARS-CoV-2 pandemic.
	
Without appropriate social distancing and PPE, there is a potential for increased exposure to SARS-CoV-2. In addition, local travel and movement restrictions could impact study visit conduct and protocol compliance.
	
 • Pfizer will work with sites to ensure an appropriate COVID-19 prevention strategy and to mitigate the impact of local travel restrictions. • Monitoring for cases of COVID-19 developing during the study, which will be reported as AEs.

Venipuncture will be performed during the study.
	
There is the risk of bleeding, bruising, hematoma formation, and infection at the venipuncture site.
	
Only appropriately qualified personnel will obtain the blood draw.

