4. STUDY DESIGN

4.1. Overall Design

This Phase 3, multicenter, randomized, observer-blind study with a 2-arm parallel design will be conducted at investigator sites in the southern hemisphere. The purpose of this study is to assess the safety and immunogenicity of BNT162b2 and SIIV given together compared to the vaccines given 1 month apart. Approximately 1126 participants will be randomized at a ratio of 1:1 into the coadministration group and the separate-administration group stratified by age group (18-49 years and 50-64 years) and by history of positive SARS-CoV-2 test result by NAAT or rapid antigen test prior to randomization (with prior history of SARS-CoV-2 and without prior history of SARS-CoV-2). A single lot of SIIV is proposed for the study, and ideally this SIIV would be recommended for use in adults 18 through 64 years of age; however, ultimately the SIIV used may be determined by supply availability.

Local reactions (redness, swelling, and pain at the injection site) occurring at the BNT162b2 or saline injection site within 7 days and systemic events (fever, headache, fatigue/tiredness, chills, vomiting, diarrhea, new or worsening muscle pain, and new or worsening joint pain) occurring within 7 days after each vaccination (Visit 1 and Visit 2) will be prompted for and collected daily by the participant in an e-diary device or application. Use of antipyretic/pain medications will also be prompted for and collected daily in the reactogenicity e-diary for 7 days after each vaccination.

AEs will be collected from the signing of informed consent through Visit 3 (approximately 1 month after Vaccination 2). SAEs will be collected from the signing of informed consent through Visit 3.

To assess immunogenicity, approximately 30 mL of blood will be collected from all participants at 3 study visits: at Visit 1 (prior to Vaccination 1); at Visit 2 (prior to Vaccination 2); and at Visit 3 (1 month after Visit 2).

Each participant will participate in the study for approximately 2 months. Based on an estimated 1- to 2-month enrollment, the study duration will be approximately 3 to 4 months. All participants will receive BNT162b2, SIIV, and saline via intramuscular injection.

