8.3.8. Adverse Events of Special Interest

AESIs are examined as part of routine safety data review procedures throughout the clinical trial and as part of signal detection processes.

All AESIs must be reported as an AE or SAE following the procedures described in [Section 8.3.1](#) through [Section 8.3.4](#). An AESI is to be recorded as an AE or SAE on the CRF. In addition, an AESI that is also an SAE must be reported using the Vaccine SAE Reporting Form.

The following events are considered AESIs:

- A confirmed diagnosis of myocarditis or pericarditis. See [Section 8.11](#) for additional procedures for monitoring of potential myocarditis or pericarditis.
- A confirmed COVID-19 diagnosis, or positive SARS-CoV-2 test result (by NAAT or rapid antigen test).

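### The only between-group AE interval for BNT162b2 with SIIV against BNT162b2 without SIIV compares different study months, so it mixes any change over time in background illness or AE reporting with the coadministration effect

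*SAP*

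**What the plan says.** The primary safety objective (protocol section 3, SAP 2.1) is to describe the safety of BNT162b2 given together with SIIV. AEs within 1 month of each vaccination are one of four primary safety endpoints.

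For Tier 1 (if any) and Tier 2 events, SAP 6.1.1.3.1 plans two between-group differences with Miettinen-Nurminen 95% CIs. Protocol 9.3.2 plans the same two for Tier 2.

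- **Contrast A:** the coadministration group's month after Visit 1 "vs 1 month after vaccination with SIV and saline at Visit 1 for the separate-administration group".
- **Contrast B:** that same coadministration month "vs 1 month after vaccination with BNT162b2 at Visit 2 for the separate-administration group".

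A preferred term is Tier 2 if at least 1% of participants in at least one group report it (SAP 3.1.1.4). Visit 2 falls "28 to 42 Days After Vaccination 1" (protocol 1.3).

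The protocol's risk table lists "Monitoring for cases of COVID-19 developing during the study, which will be reported as AEs". Protocol 8.3.8 makes this an AESI, to be recorded as an AE or SAE: "A confirmed COVID-19 diagnosis, or positive SARS-CoV-2 test result (by NAAT or rapid antigen test").

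The safety population is everyone who received any study intervention, with no exclusion for infection. SAP version 3 does exclude newly infected participants, but only from the evaluable BNT162b2 immunogenicity population.

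**The concern.** Contrast A is concurrent, but both sides received SIIV, so it shows the effect of adding BNT162b2. Contrast B is the only planned interval that shows the effect of adding SIIV to BNT162b2, and its two sides come from different study months. Randomisation balances the groups within a study month. It does not balance the first month of one group against the second month of the other. The Visit 2 side is also restricted to those who came back and were vaccinated.

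Any change between the two months is therefore part of contrast B. If background illness rises, coadministration looks safer than BNT162b2 alone. If illness falls, or participants report fewer AEs in the second month, it looks worse. The direction cannot be known in advance.

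A change over time is plausible here. The protocol describes Omicron as dominant in many countries, and the trial "will be conducted at investigator sites in the southern hemisphere" alongside seasonal influenza vaccination. COVID-19 is its own AE term and would receive this CI if it reached 1% in either group.

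**Working it through.** **1. Which contrast answers which question** (protocol Table 1, SAP 6.1.1.3.1)

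| | Month after Visit 1 | Month after Visit 2 |
|---|---|---|
| Coadministration | BNT162b2 + SIIV | saline |
| Separate administration | saline + SIIV | BNT162b2 |

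Contrast A is top left minus bottom left: same month, differing in BNT162b2. Contrast B is top left minus bottom right: differing in SIIV and in month. The top-right cell, saline in the coadministration group, enters no planned contrast.

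**2. Group size.** Protocol 9.5 gives 450 evaluable per group and 20% nonevaluable: 450 / 0.8 = 562.5, so 563 per group and 1126 in total, as stated. The documents give no power or precision for the AE contrasts. The Table 5 power concerns immunogenicity only.

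**3. How far the calendar windows overlap.** Protocol 4.1 states: "Based on an estimated 1- to 2-month enrollment, the study duration will be approximately 3 to 4 months". Participants enter on different dates, so the two windows overlap in calendar time across participants even though they never overlap within one participant. Assuming uniform accrual and a lag of 28 to 42 days, the shared calendar person-time is:

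- 18% to 27% for 1-month enrolment;
- 36% to 54% for 2-month enrolment.

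Overlap weakens a calendar trend without removing it. It does nothing to an effect tied to study month, such as declining AE reporting. The rates in step 4 are averages per study month, so any overlap is already inside them.

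**4. Size of a false difference.** Suppose vaccination has no effect and one preferred term has background rates p1 in the first study month and p2 in the second. These rates are assumptions. With n = 563 per group:

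- expected value of contrast B = p1 − p2;
- SE = √[p1(1 − p1)/n + p2(1 − p2)/n];
- P(CI excludes 0) ≈ Φ(|p1 − p2|/SE − 1.96).

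For 2% to 5%: SE = √[(0.0196 + 0.0475)/563] = 0.01092. The half-width is 1.96 × 0.01092 = 2.14 points around a false difference of 3 points. Since 0.03/0.01092 = 2.75, the probability is Φ(0.79) = 0.78. An exact binomial calculation with the score statistic, which is the Miettinen-Nurminen test at a difference of 0, gives 0.80. The reverse shift, 5% to 2%, gives the same size with the opposite sign.

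For 2% to 4%: SE = √[(0.0196 + 0.0384)/563] = 0.01015 and the half-width is 1.99 points. The probability is 0.50 by this formula and 0.51 by the exact calculation.

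For a constant 2% or 5% it is 0.05, as it should be.

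**5. Whether a same-period contrast removes the effect.** Over Vaccination 1 to Visit 3 both groups receive all three products and pass through the same two study months. With no vaccine effect and independent months, the chance of at least one event is the same in both groups. For 2% then 5% it is 1 − 0.98 × 0.95 = 6.9%. The expected difference is 0, and the score interval excludes 0 in 4.9% of trials. A simulation that adds the two monthly proportions within each group also gave no bias and about 5% false signals in every scenario, including 2% to 6% and 5% to 10%.

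**The case against.** **Detection.** A reader might infer that the plan cannot reveal a period effect. The documents do not support that. SAP 6.1.1.3.1 gives counts, percentages and Clopper-Pearson CIs after each vaccination in each group, including the saline month. SAP 6.1.1.3.2 summarises AESIs, and so COVID-19, in the same way. A rise in the second month would be visible. What is missing is a between-group interval for this comparison that is free of the rise.

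**Scope.** A reader might also extend the concern to the overall any-AE rate. The planned between-group intervals are defined for preferred terms, so no any-AE interval is specified. COVID-19 would have its own row and would not contaminate the others.

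**Consequences.** It would also go too far to say that the plan will attribute a period change to coadministration. The safety objective is descriptive. It has no margin or decision rule, and p-values arise only for Tier 1 events, of which none is identified. AEs are one of four primary safety endpoints. Both documents label the visits being compared, so the non-concurrency is disclosed.

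**Design and remedy.** No group receives BNT162b2 alone at Visit 1, so contrast B cannot be made concurrent. Nor do the two same-month excesses placed side by side replace it. The Visit 1 contrast subtracts SIIV's own AEs, and at Visit 2 the groups differ in prior vaccination. This stands and shapes the fix. It does not remove the need for an interval that randomisation protects.

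**Conclusion.** The point holds in a limited form. For BNT162b2 with SIIV against BNT162b2 without SIIV, the plan offers one between-group AE interval. It compares different study months and, on one side, only those who returned and were vaccinated. A period change goes into it in full.

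Under the assumed rates, with 563 on each side and no vaccine effect, a shift of 3 points in one preferred term makes the interval exclude 0 in about 78% of trials, and a shift of 2 points in about 51%. The documents give no monthly rates, so these figures show sensitivity and do not predict a result. Fewer participants at Visit 2 would change them somewhat. The noninferiority conclusions are not affected. The risk is that a descriptive interval on the central safety question is misread, in either direction.

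**What to change.** In SAP 6.1.1.3.1, and in protocol 9.3.2 when it is next amended, keep both contrasts and add the following for Tier 1 and Tier 2 events.

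1. A randomised same-period contrast of coadministration against separate administration: participants with the event from Vaccination 1 through Visit 3 (1 month after the last vaccination), with the Miettinen-Nurminen 95% CI. The SAE endpoint already uses this period.
2. The concurrent Visit 2 contrast: the separate-administration group after BNT162b2 against the coadministration group after saline, shown beside the Visit 1 contrast as a check on the period effect. State that prior vaccination differs between the groups at Visit 2, and that this contrast does not itself estimate BNT162b2 plus SIIV against BNT162b2.
3. A footnote marking the Visit 1 versus Visit 2 contrast as non-concurrent.

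The cost is SAP wording and one or two more descriptive columns, with no new data. The whole-period contrast compares two vaccination strategies and not a single vaccination. For COVID-19, for example, it also reflects that the coadministration group is boosted about a month earlier. It should therefore stand beside contrast B and not replace it.

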6.1.1.3.2. Supplemental Analyses

Related AEs, severe AEs, and immediate AEs (within the first 30 minutes after each vaccination) and AESIs (defined in Section 8.3.8 of the protocol) will also be summarized for each vaccination in each vaccine group.

All AEs after informed consent and prior to the first vaccination will not be included in the analyses but will be listed.

6.1.1.4. Serious Adverse Events

6.1.1.4.1. Main Analyses

- Estimand: The percentage of participants reporting SAEs from the first vaccination up to 1 month after the last vaccination ([Section 2.1](#)).
- Analysis set: Safety population ([Section 4](#)).
- Analysis time point: From the first vaccination up to 1 month after the last vaccination.
- Analysis methodology: Descriptive statistics ([Section 5.2.1](#)).
- Intercurrent events and missing data: Missing data will not be imputed except for partial AE start dates ([Section 5.3](#)).
- Reporting results: Counts, percentages, and the associated Clopper-Pearson 95% CIs of SAEs from the first vaccination up to 1 month after the last vaccination will be provided for each vaccination in each vaccine group.

